#### Actual values:

- $\circ \leq 450 \text{ (normal)}$
- 0 [450; 480]
- 0 [480; 500]
- o > 500

### Changes from baseline:

- $\circ \leq 30 \text{ (normal)}$
- 0 [30; 60]
- 0 > 60

Note: The worst-case, as defined in Section 6.4, is the highest postbaseline value and associated change.

## 14.4. Vital Signs

The following Vital Signs measurements will be reported for this study for SAF at the IA and FPA.:

- Systolic Blood Pressure (mmHg)
- Diastolic Blood Pressure (mmHg)
- Pulse Rate (bpm)
- Respiratory Rate (breaths/min)
- Oral Temperature (°C)

Vital signs parameters will be summarized using descriptive statistics at each analysis visit. Abnormalities will be presented as cross-tabulations of the abnormality at each post-baseline analysis visit.

All datapoints obtained after informed consent up to 60 days after IMP discontinuation or database cutoff will be considered.

The following summaries will be provided for vital signs data:

Vital signs parameters will be summarized using descriptive statistics at each analysis visit.

Abnormalities will be presented as cross-tabulations of the abnormality at each postbaseline analysis visit and at the worst-case analysis visit versus the baseline abnormality.

All vital signs data will be listed, but only for participants with any postbaseline abnormality.

Document: BIOSdata\argenx\Efgartigimod\HAB40220\Biostatistics\Documentation\SAP

Author: Version Number: 1.0

Version Date: 03 June 2024

Template No.: CS\_TP\_BS016 Revision 7 Reference: CS\_WI\_BS005

Page 36 of 54

# 14.4.1. Vital Signs Abnormal Criteria

Abnormal quantitative Vital Signs measurements will be identified in accordance with the following predefined abnormal criteria.

Variable	Unit	Low	Normal	High		
SBP	mmHg	< 90	90-150	> 150		
DBP	mmHg	< 45	45 – 90	> 90		
Heart rate	Bpm	< 40	40 – 100	> 100		
Body temperature	°C	< 35.8	35.8 – 37.5	> 37.5		

Note: For the worst-case analysis visits, as defined in Section 6.4, an additional category "low + high" is defined if there are both low and high postbaseline values.

## 14.5. Physical Examination

Physical examination will be assessed as defined within protocol. All datapoints obtained after informed consent up to 60 days after IMP discontinuation or database cutoff will be considered. Physical examination abnormalities will be listed.

 $\label{loss} Document: BIOS data \argenx \end{argent} Efgartigimod \argenvalue BioS data \argenvalue \argenvalue$ 

Author: Version Number: 1.0

Version Date: 03 June 2024

Template No.: CS\_TP\_BS016 Revision 7 Reference: CS\_WI\_BS005

Page 37 of 54

## 15. SECONDARY ANALYSIS

## 15.1. Efficacy Variables & Derivations

The efficacy variables are:

- Change from baseline to week 24 and week 48 in the Composite Autonomic Symptom Score 31 (COMPASS 31, modified)
- Change from baseline to week 24 and week 48 in the Malmö POTS Symptom Score (MaPS)
- Change from baseline to week 24 and week 48 in the Patient Global Impression of Severity (PGI-S)
- Patient Global Impression of Change (PGI-C) at week 24 and week 48
- Change from baseline to week 24 and 48 in the Patient-Reported Outcomes Measurement Information System (PROMIS) Fatigue Short Form 8a
- Change from baseline to week 24 and 48 in the PROMIS Cognitive Function Short Form 6a

For analyses of change from baseline, the baseline is defined as the latest measurement prior to enrollment in the OLE study. Efficacy endpoints will be analyzed using the FAS for IA and FPA. No estimands have been defined for this study.

# 15.1.1. Change from baseline to week 24 and week 48 in the Composite Autonomic Symptom Score 31 (COMPASS 31) (modified)

COMPASS 31 questionnaire is to evaluate the severity and distribution of autonomic symptoms in various autonomic nerve disorders. The 31-item questionnaire addresses 6 domains: orthostatic intolerance, vasomotor, secretomotor, bladder, pupillomotor, and gastrointestinal-mixed upper and diarrhea. The modified version (2-week recall) will be used throughout the study. The modified COMPASS 31 version used in the ARGX-113-2105 study modified the recall period to 2 weeks in contrast with the original COMPASS 31.

Participants are asked to respond to each of the item question using different, response options depending on each item, based on their perceived symptoms experience over the last 2 weeks. The response options are different depending on item content and vary from dichotomous to 7-point scale options. The modified COMPASS 31 has 6 domains that sum up to a total score of 0 to 100. Higher scores indicate a more severe degree of autonomic symptoms.

The modified COMPASS 31, scoring algorithm for each domain and total scores will be provided by external vendor. This total score will be considered for change from baseline analysis.

The analysis will be performed for the FAS for IA and FPA. Summary statistics will be provided in terms of absolute value and changes from baseline of 2105 study for each visit where no imputation performed on missing data. The

Document: BIOSdata\argenx\Efgartigimod\HAB40220\Biostatistics\Documentation\SAP

Author: Version Number: 1.0

Version Date: 03 June 2024

Template No.: CS\_TP\_BS016 Revision 7 Reference: CS\_WI\_BS005

Page 38 of 54

summary statistics for the change from baseline of 2105 study in COMPASS 31 score at each visit will also be presented by a longitudinal graph by parent treatment group.

Further charts will be produced showing the summary statustics for the change from baseline of 2105 study in COMPASS 31 score at each visit in a longitudinal graph by parent treatment group and by reverted back to QW group and non-reverted group.

For the measuring reduction in severity of COMPASS 31, summary statistics and plots for change from the parent study baseline will also be presented.

The COMPASS 31 score will also be presented by visit for 2 subgroups, subgroups are defined as changing back at any time from Q2W to QW dosing regimen (Y/N).

#### 15.1.2. Change from baseline to week 24 and week 48 in the MaPS

The MaPS score consists of 12 questions that will assess symptom burden related (tachycardia, palpitations, dizziness, presyncope) and unrelated to orthostatic intolerance (GI symptoms, insomnia, concentration difficulties). Participants will grade their symptoms for the past 7 days using a 11-point scale ranging from 0 (no symptoms) to 10 (worst possible). The items will be summed to yield a total score with a maximum value of 120 points, with higher scores indicating more severe symptoms. This total score will be derived programmatically.

For change from baseline to week 24 and week 48 in MaPS score, analysis will be presented similar to analysis proposed for COMPASS 31, MaPS will also be presented by visit for 2 subgroups (switch back from Q2W to QW=Y/N). All data will be included for subject in the IA even if it is for visits after week 24.

Additionally, a worsening will be defined as having 2 consecutive MAPS measures that are  $\geq 10$  points higher than baseline, in absence of infection/AEI. The number and percentage of patients who entered OLE and had a worsening condition will be calculated and presented by parent study treatment arm.

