### 2.3.1. Risk Assessment

Overall, available data confirm that efgartigimod IV has been well-tolerated across studies in different indications and has an acceptable safety profile.

Potential clinically significant risk	Summary of data/rationale for risk	Mitigation strategy
Serious infection	Efgartigimod reduces IgG levels, potentially hindering immune response and increasing the risk for infection.	Exclude participants with clinically significant active infection not sufficiently resolved in the investigator's opinion (Section 5.2).
		Infections are considered AESIs (Section 8.4.6). Monitor for infections and temporarily interrupt IMP dosing as specified in Section 7.1.
Infusion/injection- related reactions	All therapeutic proteins can elicit immune responses, potentially resulting in hypersensitivity or allergic reactions such as rash, urticaria, angioedema, serum sickness, and anaphylactoid or anaphylactic reactions.	Monitor participants during administration and for 30 minutes thereafter for clinical signs and symptoms of infusion reactions. Infusion/injection-related reactions are considered AEs of clinical interest (Section 8.4.7).
		If an infusion reaction occurs, interrupt the infusion and institute appropriate supportive measures. Once resolved, the infusion can be resumed and at a slower rate, if necessary.

Potential clinically significant risk	Summary of data/rationale for risk	Mitigation strategy
Infusion/injection- site reactions	Most AEs have been mild, transient injection site reactions, including erythema, pain, bruising, pruritus, burning, tenderness, edema, induration, irritation, paresthesia, numbness, and rash. Moderate injection site reactions occurring less frequently include burning, erythema, pain, and numbness. Mild to moderate headache is commonly reported.	Continuously monitor participants for injection site reactions.  Infusion/injection-site reactions are AEs of clinical interest (Section 8.4.7).

AE=adverse event; AESI=adverse event of special interest; IgG=immunoglobulin G; IMP=investigational medicinal product

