#### **8.4.6. AESIs**

An AESI is an AE of scientific and medical concern specific to the sponsor's product or program. An AESI can be serious or nonserious, related or unrelated to the IMP or study procedures. These events will be reported according to the same timeframe as that for SAEs specified in Section 8.4.1 and Section 10.3.4.

Efgartigimod treatment leads to reduced IgG levels. As low IgG levels can be associated with increased infection risks, events under the MedDRA SOC *Infections and infestations* are considered AESIs in this study. These events will be reported according to the timeframe specified in Section 8.4.1 and Section 10.3.4, with the following information provided:

- Causal pathogen
- Location of infection
- Relationship to an underlying medical condition, medical history, and concomitant medications
- Reoccurrence of a previous infection
- Any confirmatory procedure, culture, or urgent medical intervention, if applicable

Participants for whom an AESI has been reported may be temporarily interrupted from IMP treatment, as specified in Section 7.1.2.

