## **9.3.1.1.** Estimands

No treatment effect will be estimated; the outcomes that will be summarized will be presented as descriptive and as pertaining to participants having efgartigimed as administered in the OLE, with in addition any treatments administered subsequent to efgartigimed, up to the end of scheduled follow-up.

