Severity is classed as mild/moderate/severe/life-threatening/death. If a participant reports a TEAE more than once within that SOC/PT, the AE with the worst-case severity will be used in the corresponding severity summaries.

Relationship, as indicated by the Investigator, is classed as "not related" or "related". If a participant reports the same AE more than once within that SOC/ PT, the AE with the worst-case relationship to IMP will be used in the corresponding relationship summaries.

AEs leading to discontinuation of IMP will be identified by using the "Action taken with Efgartigimod/Placebo due to adverse event" from the AE page of the eCRF.

Adverse event of special interest (AESI) can be serious or nonserious, related, or unrelated to the IMP or study procedures. Infections are considered AESIs and are defined as events with a PT that falls under the MedDRA SOC 'Infections and infestations'.

Infusion/injection related reactions (IRRs) are defined as all AEs with a MedDRA PT that is listed in either:

- MedDRA Hypersensitivity SMQ broad selection
- MedDRA Anaphylactic reaction SMQ broad selection
- MedDRA Extravasation events (injections, infusions, and implants) SMQ broad selection, excluding implants and occurs within 48 hours of an infusion/injection, or within 2 days if the AE start time is not available. In case of partially missing AE start date, the AE will be considered an IRR, unless the available parts of the AE start date provide evidence it did not occur within 48 hours of an infusion/injection.

Any deaths during the study are recorded on the "Deaths Details" page of the eCRF. A death case is defined as an AE with outcome 'fatal'. Fatal events will be presented in a summary table presenting overall TEAEs and a data listing along with primary cause of death.

BIOSdata\argenx\Efgartigimod\HAB40220\Biostatistics\Documentation\SAP Document:

1.0 Author: Version Number:

> Version Date: 03 June 2024

Reference: CS WI BS005

Template No.: CS\_TP\_BS016 Revision 7

Page 31 of 54

Summary tables will only include TEAEs. However, all AEs reported during the study will be listed. Summary tables by SOC and PT will be sorted alphabetically.

An overview table of AEs will be presented to show number and percentage of participants with at least one event, and the number of events and the event rate per 100 PYFU, for the SAF at the IA and FPA for the following;

- TEAEs (IA and FPA)
- Serious TEAEs (IA and FPA)
- Grade ≥3 TEAEs (IA and FPA)

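### The count of sustained MaPS worsening leaves out worsening with infection, the drug's own AESI, so it can only equal or fall below all-cause worsening; a score-only count should stand beside it

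*SAP*

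**What the plan says.** After the by-visit MaPS summaries, SAP 15.1.2 adds one further outcome. It states that "a worsening will be defined as having 2 consecutive MAPS measures that are" at least 10 "points higher than baseline, in absence of infection/AEI". It is reported as follows: "The number and percentage of patients who entered OLE and had a worsening condition will be calculated and presented by parent study treatment arm".

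On infection, SAP 14.1 says: "Infections are considered AESIs and are defined as events with a PT that falls under the MedDRA SOC" Infections and infestations. The same section lets an AESI be serious or not, and related to IMP or not. Protocol 8.4.6 gives the reason for treating the whole SOC this way: "As low IgG levels can be associated with increased infection risks". Protocol 2.3.1 lists serious infection as a potential clinically significant risk: "Efgartigimod reduces IgG levels, potentially hindering immune response and increasing the risk for infection".

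The SAP gives no reason for the infection clause, no time window linking an infection to the two scores, and no companion count without the clause. AEI is not in its abbreviation list. The protocol's efficacy analysis section (9.3.3.1) does not define this worsening outcome, so it cannot fill the gaps.

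**The concern.** A participant whose MaPS stays at least 10 points above baseline, but who has an infection, is not counted as worsened and yet remains in the denominator. For the percentage, that participant looks the same as one who stayed well. The excluded event is not neutral: the protocol treats infection as a possible consequence of the drug's mechanism. Protocol 2.2 also notes that POTS may be related to autoimmunity preceded by infection, SARS-CoV-2 included. A sustained rise after a new infection could therefore be real worsening of the disease.

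A reader of the table is likely to take the figure as the share of participants who deteriorated on long-term efgartigimod. It is a narrower quantity. The rule also cannot be programmed as written, because two programmers could choose different windows and different meanings of AEI. SAP 4.2 bases the interim analysis on unblinded data, so an open choice could end up being made after results have been seen.

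**Working it through.** **1. Inputs.** The plan states no worsening rate and no infection rate, so it has no figure of its own for this outcome to reproduce. Its one planning number is about 38 participants, given as 90% of a parent study whose size is not stated (38/0.90 = 42.2). From the documents come the score rule, the denominator, the 7-day MaPS recall and the MaPS target days in SAP 6.3. The worsening share, the share removed and the infection rate below are assumptions.

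**2. Direction.** Let p be the share meeting the score rule and f the fraction of those removed by the clause. The denominator does not change, so:

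- reported share = p(1 - f)
- shortfall = p × f

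The reported share can never exceed p. It is strictly lower once one participant meets the score rule only with an infection present.

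| p | f = 10% | f = 25% | f = 50% |
|---|---|---|---|
| 10% | 9.0% | 7.5% | 5.0% |
| 20% | 18% | 15% | 10% |
| 30% | 27% | 22.5% | 15% |
| 40% | 36% | 30% | 20% |

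In whole participants: 8/38 = 21.1% on the score rule becomes 6/38 = 15.8% if two of the eight had an infection. With eight worseners, the chance that at least one is removed is 1 - (1 - f)^8, which is 0.57 at f = 10% and 0.90 at f = 25%.

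**3. How the missing window drives f.** Take infections at a constant rate, unrelated to worsening. Then f = 1 - exp(-rate × days/365.25). The MaPS target days are 2 weeks apart up to week 12, 4 weeks apart up to week 24, and 12 weeks apart after that. Three readings of the clause give:

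| Infection counts if it starts within | 0.5 per person-year | 1 per person-year | 2 per person-year |
|---|---|---|---|
| the two 7-day recall periods (14 days) | 2% | 4% | 7% |
| the span of two visits 12 weeks apart plus the first recall (84 + 7 = 91 days) | 12% | 22% | 39% |
| any time in 48 weeks (336 days) | 37% | 60% | 84% |

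At one assumed rate, f runs from 4% to 60% on wording alone. A positive link between infection and a rise in MaPS would make f larger.

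**4. By parent arm.** One participant is 1/38 = 2.6 points overall. The parent study randomized 2:1 (protocol section 2). With equal roll-over, the groups are about 38 × 2/3 = 25 and 38/3 = 13, so one removed worsener moves the percentage by 1/25 = 4.0 or 1/13 = 7.7 points.

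**5. AEI.** If it stands for AESI, it adds little to the word before it, because infections are the only AESI category named (protocol 8.4.6, SAP 14.1). If it stands for adverse events of clinical interest, the infusion-related reactions of protocol 8.4.7 would also remove worseners. The documents do not decide between these.

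**6. Where the same deterioration stays visible.** The by-visit MaPS changes in SAP 15.1.2 state no infection filter. PGI-S and PGI-C are each classed as improvement, no change or worsening (SAP 15.1.3 and 15.1.4), also without a filter. Infections are in the AESI tables (SAP 14.1), and switching back to weekly dosing is summarized in SAP 15.5.

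**The case against.** The strongest reply is that the clause defines a legitimate quantity. MaPS items include tachycardia, palpitations, gastrointestinal symptoms and insomnia, which an infection can plausibly produce too, so separating loss of POTS control from symptoms of infection makes sense. Keeping infected participants in the denominator is normal for a cause-specific proportion. The count is supplementary and descriptive, in a study that tests no hypothesis. The most natural reading ties the clause to the two scores themselves. With eight worseners, the 14-day reading then removes 8 × 0.019 = 0.15 to 8 × 0.074 = 0.59 of a participant on average.

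Much of this stands. An infection-free count is a fair second line, and the loss may be small or nil. Three things remain. The SAP does not state this purpose. Requiring two consecutive scores already screens out much passing illness, above all after week 24, when the scores are 12 weeks apart and each recalls 7 days; the reply has more force for the early visits 2 weeks apart. And without a score-only row nobody can see what the clause removed.

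A reader might also infer a conflict with protocol 9.3.1.1, which describes outcomes "as pertaining to participants having efgartigimed as administered in the OLE". That section does not mention infection and does not bar a cause-specific count shown beside unfiltered summaries, so no departure is established.

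**Conclusion.** The point holds as a limited one. As defined, the worsening percentage can only equal or understate all-cause sustained worsening on MaPS, and the part left out may be drug-related. The direction follows from the definition and needs no assumption. The size does: at an assumed 0.5 to 2 infections per person-year, unrelated to worsening, about 2-7% of worseners are dropped on the narrowest reading and 37-84% on the widest. It is zero if no worsener has an infection.

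Three stronger conclusions are tempting and are not supported:

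- That the figure is in fact understated by a large amount. The large losses need the reading that any infection at any time counts, and the documents give no rates.
- That the plan would hide deterioration because this is its only per-participant measure of it. PGI-S and PGI-C have unfiltered worsening categories. This is only the plan's sustained-worsening count on MaPS.
- That AEI is a slip for AESI. That is a guess, and only the sponsor can settle it.

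The protocol's MaPS endpoint, change from baseline to weeks 24 and 48, is not affected. This is a cheap improvement to one descriptive table.

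**What to change.** In SAP 15.1.2, report the number and percentage meeting the score rule alone, regardless of infection, next to the infection-free version. Give both by parent arm and overall, with the number of worseners the clause removes in each arm.

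Have the sponsor define AEI. State which infections count, for example events in the Infections and infestations SOC, and fix the window relative to the two MaPS dates: ongoing at either assessment, or starting within a stated number of days before it. Add a sentence on the purpose of the infection-free count. Settle all of this before the interim database lock.

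The cost is one extra table row and a few lines of SAP text, using data already collected. The downside for the sponsor is a worsening figure that may be slightly less favourable.

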#### 15.1.3. Change from baseline (CFB) to week 24 and week 48 in the PGI-S

Patient Global Impression of Severity (PGI-S):

- Severity of symptoms over the past week (1-week recall)
- overall experience of symptoms over the past 2 weeks (2-week recall)

are both rated on a 4-point type Likert scale, with scores ranging from 1 (none), 2(mild), 3(moderate) and 4 (severe).

Positive PGIS change (1, 2, 3) indicates worsening, while negative PGIS change (-1, -2, -3) indicates improvement while considering change from baseline to week 24 for both 1 week recall and 2 week recall results separately using the FAS for the IA.

Document: BIOSdata\argenx\Efgartigimod\HAB40220\Biostatistics\Documentation\SAP

Author: Version Number: 1.0

Version Date: 03 June 2024

Template No.: CS\_TP\_BS016 Revision 7 Reference: CS\_WI\_BS005

Page 39 of 54

#### **PGIS Change**

Improved 3 categories	CFB = -3
Improved 2 categories	CFB =-2
Improved 1 categories	CFB =-1
No Change	CFB=0
Worsened 1 category	CFB =+1
Worsened 2 categories	CFB =+2
Worsened 3 categories	CFB = +3

The number and percentage of participants with each PGI-S score will be summarized by treatment and time point, for the FAS. Number and percentages will also be presented for CFB categories for both 1 week recall and 2 week recall responses separately using the FAS for the IA.

These PGI-S score will further define as Improvement (with CFB as -3, -2 or -1), No Change (with CFB as 0) and Worsening (with CFB as +1, +2, +3).

#### 15.1.4. PGI-C at week 24 and week 48

The Patient Global Impression of Change (PGI-C) is a single item designed to capture the subject's perception of change in their overall symptom severity. Overall change in symptoms from the start of IMP to time point is rated on a 7-point Likert scale, with scores ranging from Much Better (1), Somewhat Better (2), A Little Better (3), No change (4), A Little Worse (5), Somewhat Worse (6), and Much Worse (7).

The number and percentage of participants with each PGI-C score will be summarized by treatment and time point, for the FAS for IA and FPA.

These PGI-C score will further define as Improvement (those reporting "Much better", "Somewhat better", or "A little better"), No Change (those reporting "No change") and Worsening (those reporting "A little worse", "Somewhat worse" or "Much worse").

Document: BIOSdata\argenx\Efgartigimod\HAB40220\Biostatistics\Documentation\SAP

Author: Version Number: 1.0

Version Date: 03 June 2024

Template No.: CS\_TP\_BS016 Revision 7 Reference: CS\_WI\_BS005

Page 40 of 54

